#### **11.2.1. Summaries of Adverse Event Incidence Rates for All Subjects**

Overall summary of TEAE's will be summarized by any TEAE, treatment-related TEAE, treatment-related and severe TEAE, TEAE leading to study drug discontinuation, any serious TEAE, any serious and treatment related TEAE and TEAE resulting in death. Summaries of AEs will include incidence of TEAEs and treatment-related TEAEs by MedDRA preferred term (PT) and system organ class (SOC). The TEAEs will also be summarized by severity, PT, and SOC. Subjects reporting more than one TEAE are counted once in each category at the maximum severity.

AEs with a start date during the study will be summarized. Listings of all AEs, AEs leading to discontinuation of the study, SAEs, and deaths, if any, will be provided.

#### **11.2.2. Missing and Partial AE Onset Dates**

Imputation of missing and partial dates is described in [Section 6.4.4](#).

### **11.2.3. Summaries of Adverse Incidence Rates for Serious Adverse Events (SAE), Adverse Event Dropouts, and Death**

Any SAE, dropouts, or death related to the study drug will be listed in a table by treatment group.

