6.2.6.3. Causality: Drug Relationship Assessment

The relationship of the event to the study drug should be determined by the investigator according to the following criteria:

- Definitely related: The event follows a reasonable temporal sequence from the time of drug administration that cannot be explained, follows a known or expected response pattern to the study drug, that is confirmed by improvement on stopping and reappearance of the event on repeated exposure and that could not be reasonably explained by other factors such as the patient's clinical condition, intercurrent illness, or concomitant drugs.
- Probably related: The event follows a reasonable temporal sequence from the time of drug administration, and/or follows a known response pattern to the study drug, and cannot be reasonably explained by other factors such as the patient's clinical condition, intercurrent illness, or concomitant drugs.
- Possibly related: The event follows a reasonable temporal sequence from the time of drug administration, and/or follows a known response pattern to the study drug, but could have been produced by other factors such as the patient's clinical condition, intercurrent illness, or concomitant drugs.
- Unlikely related: The event follows little or no temporal sequence from the time of drug administration that makes a causal relationship improbable and/or other factors such as the patient's clinical condition, intercurrent illness, or concomitant drugs is a more likely alternative.
- Not related: The event is most likely produced by other factors such as the patient's clinical condition, intercurrent illness, or concomitant drugs, and does not follow a known response pattern to the study drug, or the temporal relationship of the event to study drug administration makes a causal relationship unlikely.

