6.2.6.8. Adverse Event Follow-Up

All non-serious AEs that are not related or unlikely to be related to study treatment will be followed until the end of study participation. All SAEs or AEs that are considered as possibly, probably, or definitely related to treatment will be followed until resolution or stabilization.

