8.4.4.1. Adverse Events

The Medical Dictionary for Regulatory Activities (MedDRA, version 20.0) will be used to classify all AEs. Adverse event summaries will include only treatment-emergent AEs (TEAEs) by treatment group. Treatment-emergent adverse events (TEAEs) are defined as AEs that first occurred or worsened during the indicated treatment phase.

The number and percentage of patients with TEAEs will be summarized by system organ class (SOC) and preferred term (PT). Summaries of AEs by severity and relationship to the study treatment will also be provided. Serious adverse events (SAEs) and AEs resulting in discontinuation will be summarized separately in a similar manner. Patient listings of AEs and SAEs will be produced.

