### **11.2. Adverse Event Preferred Term and Body/Organ System Summary Tables**

Treatment Emergent Adverse Events (TEAEs) are defined as AEs that first occurred or worsened after the first administration of the investigational product. Adverse events are considered treatment-related if the relationship to study drug is related. A missing relationship will be imputed as related to study drug and included in the summary.

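### SAP 11.2.3 limits the by-arm table of SAEs, AE dropouts and deaths to drug-related events, which is narrower than protocol 8.4.4.1, and SAP 11.2 does not say which causality levels count as related

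*SAP*

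**What the plan says.** SAP 11.2.3 is headed as the incidence summary for SAEs, AE dropouts and deaths. Its whole content is: "Any SAE, dropouts, or death related to the study drug will be listed in a table by treatment group".

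SAP 11.2 defines the term it relies on: "Adverse events are considered treatment-related if the relationship to study drug is related". It adds a rule for gaps: "A missing relationship will be imputed as related to study drug and included in the summary".

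Protocol 6.2.6.3 has the investigator choose one of five levels: definitely, probably, possibly, unlikely or not related. Protocol 6.2.6.8 groups these for follow-up. Non-serious events that are unlikely or not related are followed to the end of participation, while "All SAEs or AEs that are considered as possibly, probably, or definitely related to treatment" are followed until they resolve or stabilise.

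Protocol 8.4.4.1 first sets out TEAE tables by SOC and PT, with splits by severity and relationship. It then says: "Serious adverse events (SAEs) and AEs resulting in discontinuation will be summarized separately in a similar manner". That sentence carries no causality condition.

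SAP 11.2.1 gives an overall summary with rows for any serious TEAE, TEAEs leading to study drug discontinuation and TEAEs resulting in death, all regardless of causality. It also provides listings of all SAEs, deaths and AEs leading to discontinuation.

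**The concern.** Two things look wrong. First, the SAP filters a table that the protocol leaves unfiltered. Second, the filter uses a term that does not match the recorded scale.

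In a blinded, placebo-controlled trial the between-arm comparison of all events needs no opinion on cause. A causality filter puts the investigator's judgement in front of that comparison. The judgement is hard here: the infants have a serious underlying disease, and both arms take vigabatrin. The protocol's definitions make a high rating difficult for grave events. The top level asks for a pattern "that is confirmed by improvement on stopping and reappearance of the event on repeated exposure", which a fatal event could rarely show. The second level requires that the patient's condition, intercurrent illness or concomitant drugs cannot reasonably explain the event. At stake is whether the report shows, by event type and arm, the serious and discontinuation events that the protocol promised to summarise.

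**Working it through.** The plan states no figure on this point, so there is none to reproduce. The check is a comparison of texts, followed by an illustration on assumed rates.

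**1. Is there an all-causality table by SOC, PT and arm?**

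| Event type | Protocol 8.4.4.1 | SAP 11.2.1 | SAP 11.2.3 | Shells and listings (SAP 14.1, 14.2) |
|---|---|---|---|---|
| SAEs | All, summarised like TEAEs (SOC, PT) | One all-causality row; full listing | Related only | Shell 12.2.2, no relatedness limit in title; listing 12.2.3 |
| AEs leading to discontinuation | All, summarised like TEAEs (SOC, PT) | One all-causality row; full listing | Related only | No summary shell; listing 12.2.5 |
| Deaths | Not named separately, but death is an SAE criterion (6.2.6.4) | One all-causality row; full listing | Related only | Shell 12.2.2; listing 12.2.4 |

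The SOC and PT tables in SAP 11.2.1 cover all TEAEs and treatment-related TEAEs, with a severity split. Serious events are inside the first of these but are not shown separately. SAP 11.2.3 is therefore the only SAP text for a dedicated SAE or discontinuation table, and it carries the filter.

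**2. What does *related* select?**

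The levels kept out of five depend on how the programmer reads SAP 11.2:

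- exact match to *related*: 0 of 5, so only events with missing causality enter, through the imputation rule;
- definitely only: 1 of 5;
- definitely, probably and possibly, as grouped in protocol 6.2.6.8: 3 of 5.

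These count labels, not events. They show only that the SAP does not settle the choice. The same undefined term drives three rows of the SAP 11.2.1 overall summary (related, related and severe, serious and related), the treatment-related SOC and PT table, and shell 12.2.4.

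**3. How much could the filter remove?**

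The documents give no SAE rate for this trial, so the rates here are assumptions. Expected patients in the table = N × share with an SAE × share passing the filter. With N = 190 (protocol 8.2):

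| Assumed share with an SAE | No filter | Three-level mapping, 10% to 50% pass | Exact match, 0% to 5% pass (missing only) |
|---|---|---|---|
| 5% | 190 × 0.05 = 9.5 | 0.95 to 4.75 | 0 to 0.48 |
| 10% | 190 × 0.10 = 19 | 1.9 to 9.5 | 0 to 0.95 |
| 20% | 190 × 0.20 = 38 | 3.8 to 19 | 0 to 1.9 |

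With the SAP's N = 180 each entry is about 5% lower (180/190 = 0.947).

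**4. An example from the documents.** Protocol 1.3.3 reports that in the sponsor's 48-week study one of 52 subjects (1.9%) discontinued because of a death judged not related to the product. A table built to the SAP 11.2.3 wording would leave that death out; the all-causality death row in SAP 11.2.1 would still count it.

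**The case against.** The strongest reply is that nothing serious disappears. SAP 11.2.1 keeps all-causality rows for serious, fatal and discontinuation TEAEs and lists every such event. Shell 12.2.2 is unrestricted in its title, a separate shell covers drug-related events, and SAP 7.1 says the templates set the content of the tables. This stands, and it limits the point. A reader might infer that the serious-event table will be nearly empty, or that the all-causality comparison of serious outcomes is discarded. The documents support neither. Near-emptiness needs an exact-match reading of *related* (or one confined to *definitely*), although protocol 6.2.6.8 offers a natural three-level grouping and missing causality counts as related. The headline comparison survives in SAP 11.2.1.

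The reply does not close the gap. One-line counts and listings are not the event-level summaries that protocol 8.4.4.1 calls for. An unrestricted shell title contradicts SAP 11.2.3 rather than correcting it. The shell list is also labelled a sample and includes an exposure table for a different drug, so it is weak authority against the text. It has no summary for discontinuations at all.

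Three smaller objections have some force:

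- The relatedness phrase could grammatically attach to deaths alone. The wider reading is more natural, and on the narrower one deaths would still be filtered.
- It goes too far to say that a death can never be rated definitely related. An event could improve on stopping, recur on re-exposure and then prove fatal.
- SAP section 1 bases the SAP on protocol version 2.0 of 30 October 2017. The supplied protocol differs from the SAP (190 patients against 180), so it may be another version, and the causality scale of version 2.0 and the CRF cannot be seen.

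**Conclusion.** SAP 11.2.3 is wrong as written. It states a causality filter that protocol 8.4.4.1 does not have and that conflicts with the SAP's own shell 12.2.2. It leaves the SAP text without an all-causality SAE or AE-discontinuation table by SOC, PT and arm. Separately, SAP 11.2 does not map the five recorded levels to *related*.

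The consequence is moderate. Safety reporting is descriptive, so no test or error rate is affected. Even under the natural three-level mapping, the assumed pass rates of 10% to 50% mean that half to nine tenths of patients with an SAE would be missing from this one table.

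The conclusion assumes that the phrase covers all three event types and that the supplied protocol's causality scale is the one recorded. If the scale differed in version 2.0, the mapping point would need rechecking. The conflict between SAP 11.2.3 and shell 12.2.2 would remain.

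**What to change.** - **SAP 11.2.3:** delete the phrase limiting the table to events related to study drug. Tabulate all SAEs, all AEs leading to discontinuation and all deaths by treatment group, SOC and PT, keeping to treatment-emergent events as in the other AE tables. Use the Safety Population by treatment actually received (protocol 8.3). Show related events as an additional display.
- **SAP 11.2:** state that definitely, probably and possibly related count as treatment-related, in line with the protocol 6.2.6.8 grouping, and keep the rule that missing counts as related.
- **SAP 14.2:** add a summary shell for AEs leading to discontinuation, and make shell 12.2.2 match the revised text.

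The cost is two SAP sentences, one shell and standard safety tables. No new data are needed. SAP section 1 allows the document to change until it is finalised before database lock.

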### **11.3. Total Duration of Therapy, Average Daily Dose, Maximum Daily Dose, Final Daily Dose of Study Medication, and Compliance**

Exposure to study medication in days will be presented for the Safety Population, by treatment category and overall. Patients are expected to complete the study drug as prescribed, however, if safety or tolerability issues arise the patient will be counted as a treatment failure and discontinued. The following parameters will be summarized by assigned treatment group:

- Total duration of study medication at any dose
- Number and percent of patients who received their full randomized dose for the duration of the study
- Compliance with prescribed dosing (Number and percent of patients who had at least one dose modification, changed, interrupted, or permanently discontinued)

Interruptions, compliance, and dose changes are not included in the calculation of duration of exposure. Total duration of study medication is defined as the number of days between date of first study medication administration to date of last study medication administration + 1.

The corresponding listing will present first/last dose dates, does the subject complete the treatment duration, reason for end of treatment and duration of exposure (days).

In addition, dose modifications will be summarized by treatment and overall in terms of:

- Number of subjects with at least one dose modification (as defined [Section 14.1](#))
- Number of subjects with at least one dose changed
- Number of subjects with at least one dose interrupted
- Number of subjects with dose permanently discontinued
- Number of subjects per reason of dose modification
  - o Adverse event
  - o Lack of efficacy
  - o PK-analysis result
  - o Other

A patient who experiences several dose modifications for the same reason will be counted only once for this reason. A patient who experiences several dose modifications due to different reasons will be counted once for each reason.

## 11.4. Concomitant and Other Medications

Concomitant Medications will be summarized using WHO-DD version March 2017 preferred terms (PT). Any medication/therapy that stops at or after this time or with missing stop dates is considered concomitant medication/therapy. Listings and summaries will be presented separately for the Safety Population.

### 11.4.1. Missing and Partial Concomitant and Other Medication Start and Stop Dates

Imputation of missing and partial dates is described in [Section 6.4.4](#).

## 11.5. Routine Laboratory Data

Clinical laboratory findings will be summarized for all subjects in the Safety Population for observed values and change from baseline by visit. Shifts from baseline according to normal range criteria will also be presented for all subjects in the Safety Population.

Quantitative laboratory measurements reported as “< X”, i.e. below the lower limit of quantification (BLQ), or “> X”, i.e. above the upper limit of quantification (ULQ), will be converted to X for the purpose of quantitative summaries, but will be presented as recorded, i.e. as “< X” or “> X” in the listings.

For Hematology the following parameters will be summarized: *Platelet Count, White Blood Cell Count (WBC), Neutrophils (Percent), Neutrophils (Absolute), Lymphocytes (Percent), Lymphocytes (Absolute), Eosinophils (Percent), Eosinophils (Absolute), Basophils (Percent), Basophils (Absolute), Monocytes (Percent), Monocytes (Absolute), Hemoglobin and Hematocrit.*

For Serum Chemistry the following parameters will be summarized: *Total Protein, Albumin, Creatinine, Blood Urea Nitrogen, Uric Acid, Total Bilirubin, Direct Bilirubin, Alkaline Phosphatase, Aspartate aminotransferase (AST), Alanine aminotransferase (ALT), Gamma glutamyl transferase (GGT), FSH, Glucose, Calcium, Chloride, Bicarbonate, Sodium, Potassium and Phosphorus.*

The clinical laboratory data for each visit will be listed and summarized.

## 11.6. Vital Signs

Vital signs will be summarized for all subjects in the Safety Analysis Population for observed values and change from baseline as appropriate by visit for the following parameters: *Systolic Blood Pressure, Diastolic Blood Pressure, Pulse Rate, Respiratory Rate, and Temperature.*

Shifts from baseline according to normal and abnormal criteria will also be presented for all subjects the Safety Population.

### 11.6.1. Vital Signs Markedly Abnormal Criteria

Markedly abnormal quantitative Vital Signs measurements will be identified in accordance with the following predefined markedly abnormal criteria:

Variable	Unit	Low	High
SBP	mmHg	≤ 90 mmHg AND change from baseline ≤ -20 mmHg	≥ 180 mmHg AND change from baseline ≥ 20 mmHg

Variable	Unit	Low	High
DBP	mmHg	$\leq 50$ mmHg AND change from $\leq -15$ mmHg	$\geq 105$ mmHg AND change from baseline $\geq 15$ mmHg
Heart rate	Bpm	$\leq 50$ bpm AND change from baseline $\leq -15$ bpm	$\geq 120$ bpm AND change from baseline $\geq 15$ bpm
Body temperature	$^{\circ}\text{C}$	NA	$\geq 38.3$ $^{\circ}\text{C}$ AND change from baseline $\geq 1.1$ $^{\circ}\text{C}$

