3.2.1. Inclusion Criteria

All patients must satisfy the following criteria to be considered for study participation:

1. Parent(s)/caregiver(s) fully comprehend and sign the informed consent form, understand all study procedures, and can communicate satisfactorily with the investigator and study coordinator, in accordance with applicable laws, regulations, and local requirements.
2. Male or female between 1 months to 24 months of age (inclusive) at time of consent.
3. Clinical diagnosis of infantile spasms, confirmed by video-EEG analysis (including at least one cluster of electroclinical spasms [≥ 3 in any 10-minute epoch]) and hypsarrhythmia) obtained during the Screening Period and read by a central reader.
4. General good health (defined as the absence of any clinically relevant abnormalities as determined by the investigator) based on physical and neurological examinations, medical history and clinical laboratory values completed during the Screening Visit (Visit 1).
5. In the opinion of the investigator, the parent(s)/caregiver(s) is (are) willing and able to comply with the study procedures and visit schedules.

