8.1.3. Safety Endpoints

The safety endpoints of this study are the incidence of treatment-emergent AEs (TEAEs), clinical laboratory assessments, vital signs (blood pressure, pulse rate, respiration rate, and temperature), physical and neurological examination assessments, medical history, and prior and concomitant medications, liver enzymes, and serum bilirubin.

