## 3.2. Selection of Study Population

### 3.2.1. Inclusion Criteria

#### Diagnosis and main criteria for inclusion:

Patients will be male and female patients between 3 and 12 months of age (inclusive), with a new clinical diagnosis of Infantile Spasms, confirmed by video-EEG analysis during the Screening Period, have adequate renal and hepatic function and who meet all the inclusion and none of the exclusion criteria. Parent(s)/caregiver(s) must be able to understand and provide written consent.

All patients must satisfy the following criteria to be considered for study participation:

1. Parent(s)/caregiver(s) fully comprehend and sign the informed consent form, understand all study procedures, and can communicate satisfactorily with the investigator and study coordinator, in accordance with applicable laws, regulations, and local requirements.
2. Male or female between 3 months to 12 months of age (inclusive) at time of consent.
3. Clinical diagnosis of infantile spasms, confirmed by video-EEG analysis (including at least one cluster of electroclinical spasms [ $\geq 3$  in any 10-minute epoch]), hypsarrythmia or a pattern of epileptic encephalopathy) obtained during the Screening Period and read by the Investigator.
4. General good health (defined as the absence of any clinically relevant abnormalities as determined by the investigator) based on physical and neurological examinations, medical history and clinical laboratory values completed during the Screening Visit (Visit 1).
5. In the opinion of the investigator, the parent(s)/caregiver(s) is (are) willing and able to comply with the study procedures and visit schedules.

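### The SAP's fixed vital-sign limits are not adjusted for infant age; under assumed infant values, the high-systolic and low-heart-rate flags would miss almost all or most readings even after large true shifts

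*SAP*

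**What the plan says.** SAP 11.6.1 opens: "Markedly abnormal quantitative Vital Signs measurements will be identified in accordance with the following predefined markedly abnormal criteria". Each limit combines an absolute value with a change from baseline, and both must be met:

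| Variable | Low flag | High flag |
|---|---|---|
| SBP (mmHg) | at most 90, fall of at least 20 | at least 180, rise of at least 20 |
| DBP (mmHg) | at most 50, fall of at least 15 | at least 105, rise of at least 15 |
| Heart rate (bpm) | at most 50, fall of at least 15 | at least 120, rise of at least 15 |
| Temperature (°C) | none | at least 38.3, rise of at least 1.1 |

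The systolic entries, for example, read "≤ 90 mmHg AND change from baseline ≤ -20 mmHg" and "≥ 180 mmHg AND change from baseline ≥ 20 mmHg". The low-DBP entry leaves out the word baseline.

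Protocol 3.2.1 admits "Male or female between 1 months to 24 months of age (inclusive) at time of consent". SAP 3.2.1 has "Male or female between 3 months to 12 months of age (inclusive) at time of consent". Neither document gives infant reference ranges or a reason for the limits.

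Protocol 8.1.3 lists among the safety endpoints "vital signs (blood pressure, pulse rate, respiration rate, and temperature"; the SAP table has no respiration row. SAP 11.6 separately plans observed values and changes by visit, and shifts between normal and abnormal, without defining those two terms.

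**The concern.** A flag table is useful if it picks out unusual individual readings and leaves ordinary ones alone. A single set of limits for patients of 1 to 24 months, with no source, gives no assurance of either.

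The rule's own structure raises the doubt. The change part for low heart rate asks for a fall of 15 bpm, but from a baseline of 115 to 135 bpm the absolute part needs a fall of 65 to 85. The change part for high SBP asks for a rise of 20 mmHg, but from 80 to 95 mmHg the absolute part needs 85 to 100. If typical infant values lie there, the absolute part decides everything and the change part is idle. For high heart rate and low SBP the reverse may hold.

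At stake is how the safety tables are read: zero counts for high pressure or low heart rate would carry almost no information. Low heart rate is also a direction that the protocol itself raises. Section 1.2.1 reports lower heart rates in treated male monkeys in the first month of a 90-day oral study.

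Other entries suggest a re-used template: suicide and pregnancy as discontinuation reasons (SAP 8), and a pregnancy listing and a dronabinol exposure table (SAP 14.2).

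**Working it through.** The plan states no figure to reproduce. The limits come from SAP 11.6.1; all distributions below are assumptions.

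**Model.** Each infant has a true mean drawn from a normal distribution, and each reading adds independent normal visit-to-visit error. Baseline is one reading. A flag needs both parts of the rule.
- Heart rate: mean 115 to 135, between-infant SD 12, visit SD 8 to 15.
- SBP: mean 80 to 95, between-infant SD 7, visit SD 6 to 10.
- Readings: 5 after first dose (Day 1 post-dose and Visits 3 to 6 in the protocol's Schedule of Events), or 8 with Visits 7 to 9. The SAP's visit text gives 4 and 7.

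**High SBP, true shift +40 mmHg.** The chance of meeting the absolute part bounds the flag rate.
- SD of one reading: √(7² + 6²) = 9.22 to √(7² + 10²) = 12.21.
- Most favourable case: (180 − 135)/12.21 = 3.69, or 0.011%.
- Least favourable case: (180 − 120)/9.22 = 6.51, effectively zero.

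**Low heart rate, true shift −40 bpm.**
- SD of one reading: √(12² + 8²) = 14.42 to √(12² + 15²) = 19.21.
- Most favourable case: (50 − 75)/19.21 = −1.30, or 9.7%.
- Least favourable case: (50 − 95)/14.42 = −3.12, or 0.09%.
- Simulating the full rule gives about 0.1% to 10% per reading, and at least one flag over 5 readings in 0.3% to 31% of infants. With no shift the latter is at most about 0.2%.

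**High DBP.** From an assumed mean of 40 to 60 mmHg, reaching 105 needs a rise of 45 to 65, against 15 in the change part. With SD 8 to 10 and no effect, the chance is at most 3.4 in a million per reading. No shifted case was run for DBP.

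**High heart rate, no drug effect.**
- At or above 120 at baseline: 36% to 85% of infants.
- Change part alone, per reading: 15/(8√2) = 1.33, or 9.2%, to 15/(15√2) = 0.71, or 24.0%.
- Full rule, simulated: 6.0% to 22.9%. At mean 115 the absolute part removes about a third of the change flags (6.0% against 9.2%); at mean 135 it removes under 5% (22.9% against 24.0%).
- At least one flag: about 20% to 55% of infants over 5 readings, 26% to 64% over 8.

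**Low SBP, no drug effect.**
- At or below 90 at baseline: (90 − 95)/9.22 = −0.54, or 29%, to (90 − 80)/9.22 = 1.08, or 86%.
- Change part alone, per reading: 20/(6√2) = 2.36, or 0.9%, to 20/(10√2) = 1.41, or 7.9%.
- Full rule, simulated: 0.7% to 7.7%.
- At least one flag over 5 readings: 3% to 24% of infants.

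**Does this background hide a drug effect?** In the same model a +10 bpm shift raises the high-heart-rate flag from 20–55% to 60–75% of infants. A −10 mmHg shift raises the low-SBP flag from 3–24% to 32–55%. The arms would separate.

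**Wider ranges.** A second calculation used heart-rate means of 100 to 140 with SD 10 to 20, and SBP means of 75 to 105 with SD 8 to 15. With no effect, the chance of 50 bpm or less is at most 0.6% per reading, and of 180 mmHg or more at most 3 in ten million.

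**The case against.** The strongest objection is that the argument rests on infant values found in neither document. That stands as a limit on the numbers: they are conditional, and wide for three of the four flags. The remoteness of the high-SBP and low-heart-rate limits holds over every range tried. The lack of age adjustment and of any source is plain on the page.

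The second objection is coverage. SAP 11.6 gives observed values and changes by visit for all vital signs, including respiration rate, and a vital-signs listing is planned (SAP 14.1). A mean shift, or one unusual reading, can be seen there. This is real mitigation but incomplete: visit summaries can hide individual outliers, and the shift tables rest on undefined criteria.

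A reader might infer more than the documents support:
- *An ordinary steady heart rate above 120 is flagged.* It is not, without a rise of at least 15 bpm.
- *High pressure or slow heart rate can never be flagged.* Values beyond the limits with the required change are flagged; the point is how rarely that would happen.
- *Background flags bury a cannabidiol effect.* They arise in both arms, and the shifted cases above show separation.
- *Empty counts will be presented as reassurance.* The sample display list in SAP 14.2 names no markedly abnormal table, so this is conjecture.
- *Respiratory arrest in monkeys (Protocol 1.2.1) shows the respiration gap to be dangerous.* Those events followed a single high intravenous dose. The 90-day oral study reported no deaths or adverse physiological effects. The case for a respiration criterion is simply that it is a named endpoint.

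**Conclusion.** The concern holds as a moderate weakness in the safety displays. One fixed, unsourced set of limits is applied to infants of 1 to 24 months (3 to 12 in the SAP). Under the assumed means and SDs, the high-SBP flag is almost blind to a true +40 mmHg shift (at most about 0.01% of readings). The low-heart-rate flag catches about 0.1% to 10% of readings after a true −40 bpm shift. High DBP looks similarly remote with no effect, but its sensitivity was not tested. High heart rate and low SBP work largely as change flags, less so for heart rate near a mean of 115. Respiration rate has no criterion.

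Safety analyses are descriptive (Protocol 8.4.4), so the primary analysis, type I error and power are untouched. Calling the limits adult values, or naming a particular infant reading as abnormal, would need reference data that the documents do not contain. The template remnants make carry-over plausible but do not prove it.

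**What to change.** Before database lock and unblinding, which SAP section 1 allows:
- Replace the 11.6.1 table with age-banded limits for SBP, DBP, heart rate and respiration rate, or with age-specific z-scores, from one paediatric reference named in the SAP. Keep the change-from-baseline condition.
- Apply the band for age in months at each reading. Cover the protocol's range from 1 month, and let the top band run past 24 months. A patient aged 24 months at consent can be 14 + 90 = 104 days older by Day 90.
- Use the same reference to define normal and abnormal for the shift tables in SAP 11.6.
- Complete the low-DBP entry so that it names baseline.
- Add the resulting table to the display list in SAP 14.2.

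These are analysis flags only and imply no clinical management rule.

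The cost is SAP wording, a lookup table and a new age derivation, since SAP 6.2 calculates age in whole years while SAP 9.1 reports months. No new data are needed.
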